
subsequent treatment cycles (Extension Phase).
 
The study-specific procedures include: physical examination, vital signs, 12-lead electrocardiogram (ECG), performance status, clinical laboratory tests, adverse events (AEs), concomitant medication and patient compliance.
 
Patients discontinuing the study will attend an End of Study Visit, 4 weeks after the last administration of study drug.
 
Intensive PK sampling will be performed on Days 0 and 28 in all patients enrolled in Stage 1. Sparse PK sampling will be performed on Days 28, 42, and 56 in all patients enrolled in Stage 2.
 
All patients who discontinue from study drug, but consent to be followed up for survival status, will be followed up by telephone contact every 3 months, for a maximum of 6 months from the date of last administration of study drug or death, whichever occurs first.
 
Tumor assessments will be performed at Screening, Day 42 and Day 84 using the Response Evaluation Criteria in Solid Tumors (RECIST) criteria version 1.1. Tumor assessments will be performed every 12 weeks during the Extension Phase.
 
The primary efficacy endpoint is progression-free survival (PFS) rate at 12 weeks, which is defined as the proportion of patients alive and progression-free at Week 12. Patients will be progression-free if they have no evidence of progressive disease (defined according to RECIST guidelines, version 1.1) from the start of treatment to Week 12.
 
The study uses a two-stage design seeking to detect a true PFS rate of more than 35% in the overall (unselected) population and 40% within the KRAS tumor mutation positive and negative strata. Thirty evaluable patients (15 in each stratum) will be treated initially (Stage 1), with expansion to a maximum of 60 evaluable patients (Stage 2). The rules for continuing the overall study and individual stratum are given in the Statistical Methods below.
 
An Independent Data Monitoring Committee will act in an advisory capacity to monitor patient safety and efficacy data from the study. The members will be selected on the basis of relevant experience and understanding of clinical research and the issues specific to the therapeutic area, as well as previous data monitoring committee experience.
		

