Patients will attend study visits on Days 0, 14, 28, 42, 56 and 84 during the first 12-week treatment cycle, every 4 weeks during the second, third, and fourth treatment cycles (Extension Phase); and every 12 weeks during subsequent treatment cycles (Extension Phase). The study-specific procedures include: physical examination, vital signs, 12-lead ECG, performance status, clinical laboratory tests, AEs, concomitant medication and patient compliance. The schedule of assessments is presented in [Table 9.1](#).

Patients discontinuing study drug will attend an End of Study (EOS) Visit, 4 weeks after the last administration of study drug. In the event that a patient is scheduled to start a new treatment earlier than 3 weeks after the last dose of study drug, the EOS Visit should occur before the start of the new treatment and the reason documented.

Intensive PK sampling will be performed on Days 0 and 28 in all patients enrolled in Stage 1. Sparse PK sampling will be performed on Days 28, 42, and 56 in all patients enrolled in Stage 2.

All patients who withdraw from the study drug, but consent to be followed up for survival status, will be followed up by telephone contact every 3 months, for a maximum of 6 months from the date of last administration of study drug or death, whichever occurs first.

Tumor assessments will be performed at Screening, Days 42 and 84 using the Response Evaluation Criteria in Solid Tumors (RECIST) criteria, version 1.1 (see [Appendix 1](#)). Tumor assessments will be performed every 12 weeks during the Extension Phase.

The primary efficacy endpoint is progression-free survival (PFS) rate at 12 weeks, which is defined as the proportion of patients alive and progression-free at Week 12. Patients will be progression-free if they have no evidence of progressive disease (defined according to RECIST guidelines, version 1.1) from the start of treatment to Week 12.

The study uses a two-stage design seeking to detect a true PFS rate of more than 35% in the overall (unselected) population and 40% within the KRAS tumor mutation positive and negative strata. Thirty evaluable patients (15 in each stratum) will be treated initially (Stage 1), with expansion to a maximum of 60 evaluable patients (Stage 2). The rules for continuing the overall study and individual stratum are provided in [Section 14.2](#).

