- ¹⁰ All Screening procedures and laboratory results must be available and reviewed before the patient receives the first dose of study drug. Study drug should be taken at 8-hour intervals. The time of study drug administration should be recorded in the patient diary.
- ¹¹ Intensive PK sampling will be performed on Days 0 and 28 in all patients enrolled in Stage 1. Samples will be taken 30 minutes prior to and 0.5, 1, 2, 3, 4, 6, and 8 hours after the first dose on Day 0, and immediately before and 0.5, 1, 2, 3, 4, 6, and 8 hours after the first dose on Day 28. Sparse PK sampling will be performed on Days 28, 42, and 56 in all patients enrolled in Stage 2. At least two samples will be collected on each occasion, one of which will be a trough concentration (30 minutes prior to

dosing and approximately 8 hours after the last dose on the prior day). At least one sample per patient will be timed to coincide with the peak concentration (approximately 3 hours after dosing). The remainder may be taken at any time during the dosing interval.

- ¹² Patients must be followed for AEs from the date of informed consent until resolution or stabilization, alternative treatment for NSCLC is started, 6 months after last dose of study drug, or loss to follow-up, whichever occurs first. In the event of serious or study drug-related toxicities, the patient will be followed until resolution or stabilization. Safety follow-up data may be collected by telephone contact every 3 months after the EOS Visit.
- ¹³ Day 0 evaluation to be performed before the patient receives the first dose of study drug.
- ¹⁴ All patients who withdraw from the study drug, but consent to be followed up for survival status, will be followed up by telephone contact every 3 months, for a maximum of 6 months from the date of last administration of study drug or death, whichever occurs first..

The schedule of blood samples that will be drawn for each patient is presented in [Table 9.2](#).

Table 9.2 Schedule of Blood Sampling

Day	Sample No.	Time Schedule (hour)	Time* (hhmm)	Time Window	Activity
Stage 1					
0	N/A	-1	0700		Patient registration
0	N/A	-0.5	0730		Take blood for laboratory test
0	1	-0.5	0730		Take pre-dose sample
0	N/A	-0.25	0745		Take meal or light snack
0	N/A	0	0800		Take dose
0	2	0.5	0830	± 5 min	
0	3	1	0900	± 10 min	
0	4	2	1000	± 15 min	
0	5	3	1100	± 20 min	
0	6	4	1200	± 20 min	
0	7	6	1400	± 20 min	
0	8	8	1600	± 20 min	
28	N/A	-1	0700		Patient registration

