9.1.3.8 End of Study (EOS) Visit (± 7 days)

Patients will attend an EOS Visit, 4 weeks after the last administration of study drug. In the event that a patient is scheduled to start a new treatment earlier than 3 weeks after the last dose of study drug, the EOS Visit should occur before the start of the new treatment and the reason documented.

- Record concomitant medications
- Perform physical examinations
- Obtain vital signs
- Perform ECOG performance status evaluation
- Perform 12-Lead ECG examinations
- Perform clinical laboratory tests (hematology, biochemistry, and urinalysis)
- Tumor assessments (radiological and clinical tumor assessments). Tumor assessment does not need to be performed at the EOS Visit if this was conducted at the Day 84 Visit. For patients participating in the Extension Phase, the tumor assessment does not need to be performed at the EOS Visit if it has been assessed within 8 weeks of the EOS Visit.
- Perform drug accountability
- Record AE and grade possible toxicity. Safety follow-up data may be collected by telephone contact every 3 months after the EOS Visit.
- Calculate patient compliance
- Perform EORTC QLQ

- All patients who withdraw from the study drug, but consent to be followed up for survival status, will be followed up by telephone contact every 3 months, for a maximum of 6 months from the date of last administration of study drug or death, whichever occurs first.

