9.3.3 Removal of Patients from Study or from Study Treatment

Patients may withdraw their consent to participate in the study and investigators may withdraw patients at any time without prejudice. Patients will be withdrawn from the study or study treatment if any of the conditions set below has occurred:

1. Documented disease progression according to the response criteria
2. Unacceptable toxicity
3. Patient decides to withdraw his/her informed consent
4. Investigator considers that the patient is no longer physically and/or psychologically able to remain in the study

5. Patient has developed a condition that requires treatment with a medication prohibited by the protocol
6. Patient develops adverse effects that the investigator considers a permanent cessation of the study drug is necessary
7. Non-compliance with study drug, protocol requirements, or study-related procedures
8. Patient's treatment is interrupted for more than 1 week and the investigator and Medical Monitor considers a permanent cessation of the study drug is necessary

The investigators should complete the evaluation items for the EOS Visit upon a patient's withdrawal. Tumor assessment does not need to be performed at the EOS Visit if this was conducted at the Day 84 Visit. For patients participating in the Extension Phase, the tumor assessment does not need to be performed at the EOS Visit if it has been assessed within 8 weeks of the EOS Visit. This does not include a patient who has not been treated by the study drug, such as withdrawal at Screening or at Baseline. Only the electronic Case Report Form (eCRF) required data should be completed. All patients who are withdrawn or removed will not be replaced in this study.

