10.4 Extension Phase

After the first 12-week treatment cycle, patients who are progression-free will be eligible to receive further (12-week) treatment cycles with antroquinonol in the Extension Phase.

Patients participating in the Extension Phase will follow a schedule similar to that of the first 12-week treatment cycle, except no PK samples will be drawn. Patients will attend visits every 4 weeks (± 7 days) during the second, third, and fourth treatment cycles. After completion of the fourth treatment cycle, patients will attend visits every 12 weeks (± 7 days).

Patients may continue in the Extension Phase until documented evidence of disease progression, unacceptable toxicity, non-compliance or withdrawal of consent by the patient, or the investigator decides to discontinue treatment, whichever comes first.

If there is Grade 3 or 4 toxicity, the patient's dose will drop down to the next lower dose according to the Dose Modification and Toxicity Management Guidelines in [Section 10.5](#).

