14.2.1 Analysis Populations

The primary analysis will be performed on the evaluable population. The evaluable population will consist of all enrolled patients who receive at least one dose of antroquinonol and have a valid baseline tumor assessment. A valid baseline assessment is defined as a readable scan (one in which the images are of high enough quality to permit accurate assessment of the tumor) performed within 14 (\pm 7) days of the date of first administration of study drug. For the efficacy analysis, enrollment will continue until the target number of evaluable patients has been enrolled.

The full analysis set (FAS) and PPS will be used for supportive efficacy analyses. The FAS will consist of patients in the evaluable population who have at least one post-baseline tumor

assessment. The PPS will consist of patients in the FAS who do not have major protocol violations.

The PK population will consist of patients in the first stage who have an evaluable PK profile, defined as a profile from which at least one of the PK parameters stated as endpoints can be estimated, and no protocol deviations that would affect the PK of antroquinonol.

The PopPK population will consist of patients with at least two plasma concentrations and sufficient and reliable dosing histories.

The Safety population will comprise all patients who are treated with at least one dose of study drug.

The PRO population will consist of all patients who have completed the QoL Questionnaire on Day 0 and on at least one occasion after the first administration of study drug.

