14.2.2.2 Secondary Efficacy Analysis

The FAS and PPS will be used for the secondary efficacy analyses. The secondary efficacy endpoints comprise the following: ORR, DCR, DR, PFS, OS and TTP.

The ORR is defined as the proportion of patients whose best overall response is either CR or PR according to RECIST version 1.1. The best overall response is the best response recorded during the first 12-week treatment cycle.

The DCR is defined as the proportion of patients with a documented CR, PR and SD during the first 12-week treatment cycle according to the RECIST version 1.1. For both ORR and DCR, 95% two-sided CIs will be presented.

The DR is defined as the interval between the date of the first observation of tumor response (CR or PR) and the date of disease progression or death. The DR will be summarized using Kaplan-Meier methods and displayed graphically where appropriate. The DR will be calculated for the subgroup of patients with tumor response (CR or PR).

If the number of patients with a documented CR or PR is small then only descriptive statistics or listings will be presented.

Progression-free survival is defined as the time from the date of first administration of study drug to objective tumor progression by RECIST version 1.1 or death due to any cause, whichever occurs first. The censoring rule for PFS will be described in the SAP.

Overall survival is defined as the time from the date of first administration of study drug to death from any cause. The censoring rule for OS will be described in the SAP.

Time to progression is defined as the time from the date of first administration of study drug to objective tumor progression by RECIST version 1.1. The censoring rule for TTP will be described in the SAP.

Objective response rate and DCR will be reported with category counts, percentage and 95% CIs. PFS, OS and TTP will be evaluated using Kaplan-Meier estimates and curves will be generated based on these estimates.

Time-to-event endpoints will be re-analyzed when all patients have completed the Extension Phase.

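### Overall survival is planned only in patients with a post-baseline scan, which removes early deaths; survival calls that end 6 months after the last dose add a smaller problem late in the curve

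*Protocol*

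**What the plan says.** **Analysis set.** Protocol Section 14.2.2.2 assigns the secondary efficacy endpoints, OS among them, to the FAS and per-protocol set (PPS), and states that "PFS, OS and TTP will be evaluated using Kaplan-Meier estimates and curves will be generated based on these estimates". Section 14.2.1 says: "The FAS will consist of patients in the evaluable population who have at least one post-baseline tumor" assessment. The PPS is a subset of the FAS. The evaluable population needs only one dose and a valid baseline scan. Under Section 14.2.2.1 an evaluable patient who dies or leaves without the required scan counts as a failure in the primary analysis.

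**Survival follow-up.** OS runs from first dose, but the calls are anchored on the last dose. Section 9.1.1 has consenting patients who are off drug "followed up by telephone contact every 3 months, for a maximum of 6 months from the date of last administration of study drug". The same limit stands in the Synopsis, in footnote 14 of Table 9.1 ("for a maximum of 6 months from the date of last administration of study drug or death") and in Section 9.1.3.8 ("All patients who withdraw from the study drug, but consent to be followed up for survival status").

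**What ends treatment.** The first ground in Section 9.3.3 is "Documented disease progression according to the response criteria". Section 10.4 says "Patients may continue in the Extension Phase until documented evidence of disease progression" or one of the other listed reasons. Scans fall on Days 42 and 84, then every 12 weeks.

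**Status of OS.** Section 14.2.2 limits formal testing to the primary endpoint. Section 14.2.2.2 leaves the OS censoring rule to the SAP and plans a re-analysis after the Extension Phase.

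**The concern.** OS needs no scan. Requiring one means a patient must live, and stay in the study, long enough to be imaged before counting. Early deaths are removed from both numerator and denominator, and for deaths the bias has one direction. The primary analysis of the same trial handles these patients the opposite way.

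The follow-up limit works differently. Each patient's OS follow-up is time on drug plus 6 months. Since drug usually stops at progression, patients who progress early also leave survival follow-up early. Kaplan-Meier assumes that censoring is unrelated to prognosis, and late in the curve that may fail.

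With no control arm, the OS curve is read on its absolute level, so an upward shift goes straight into the reader's impression of the drug.

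**Working it through.** **1. The plan's own figures.** The only error rates stated are for the two-stage PFS design. They reproduce: stratum alpha 0.0276 and power 0.9049 (stated 2.8%, 90.5%); overall alpha 0.0279 and power 0.9558 (stated 2.8%, 95.6%). They are not in dispute. No OS median, rate or event count is given, so every survival input below is an assumption except 12-week PFS, set at the protocol's 35% and 15%.

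**2. Share dropped from the FAS.** Assume exponential PFS, 15% of PFS events being deaths without progression, and no scan before Day 42 in those patients. Day 42 is half of 12 weeks, so the dropped share is d = 0.15 × (1 − √p).
- p = 0.35: 0.15 × (1 − 0.592) = 6.1%
- p = 0.15: 0.15 × (1 − 0.387) = 9.2%

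A shared gamma frailty of variance up to 0.5 (early progressors also die sooner) raises these to about 7% and 10%.

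**3. Effect on 6-month OS.** All dropped patients are dead by 6 months, so FAS survival is S/(1 − d) and the excess is S·d/(1 − d). True S(6) follows from the PFS rate λ = −ln(p)/2.76 per month (12 weeks = 2.76 months) and the post-progression rate μ = ln 2/median: S(6) = 0.85 × (λe^(−6μ) − μe^(−6λ))/(λ − μ) + 0.15 × e^(−6λ).

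| 12-week PFS | Post-progression median | True S(6) | d | Excess |
|---|---|---|---|---|
| 35% | 3 months | 42.2% | 6.1% | +2.8 points |
| 35% | 6 months | 58.8% | 6.1% | +3.8 |
| 15% | 3 months | 31.6% | 9.2% | +3.2 |
| 15% | 6 months | 51.1% | 9.2% | +5.2 |

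With frailty the upper ends are about +4.0 and +5.6, so the overall range is about 3 to 5.5 points. For scale, at S = 55.9% and N = 60 the standard error is √(0.559 × 0.441/60) = 6.4 points. If nobody goes unscanned, d = 0 and so is the excess.

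**4. A second set of assumptions.** Suppose 10% of patients have no post-baseline scan (median 1.5 months to death) and the median after stopping is 4 to 9 months. The 6-month excess is then +3.8 to +7.3 points. The top value (74.2% true, 81.5% in the FAS) exceeds its standard error, √(0.742 × 0.258/60) = 5.6.

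**5. Where the follow-up limit starts to matter.** It cannot censor anyone before 6 months from first dose. A patient stopped at the Day 42 scan is followed to 42/30.4 + 6 = 7.4 months, and one stopped at Day 84 to 84/30.4 + 6 = 8.8 months. Only stops before the first scan, for example for toxicity, can censor between 6 and 7.4 months.

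**6. Kaplan-Meier bias at 12 months.** Simulation of 400,000 patients per scenario: drug stopped at the protocol's scans, post-progression medians 3, 4 or 6 months, frailty variance 0, 0.25 or 0.5, 0% or 15% of PFS events being deaths, full consent to follow-up.
- To about 7.3 months: no bias.
- 12 months, no shared prognosis: about 0 to +1.2 points.
- 12 months, shared prognosis: +1.7 to +4.4 (35% PFS) and +2.1 to +6.3 (15% PFS), below one standard error at N = 60.

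Another dependence model (survival after stopping scaled by 0.67, 1 or 1.5 according to time on drug; medians 4 to 9 months), with scenarios with and without that dependence, spans +0.4 to +6.8.

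**7. The two effects together.** One scenario of that second model: 35% PFS, median 6 months after stopping, early progressors dying sooner, 10% unscanned.

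| | True | Evaluable set, planned follow-up | FAS, planned follow-up |
|---|---|---|---|
| 12-month OS | 34.9% | 40.2% | 44.2% |
| Median OS (months) | 8.4 | 8.7 | 10.2 |

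Here the follow-up limit moves the median by 0.3 months and the FAS restriction by a further 1.5.

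**The case against.** The case for leaving the plan alone is reasonable. OS is secondary and untested in a phase II trial of at most 60 patients, and short survival follow-up is a resource choice. Entry requires a life expectancy of at least 3 months. Early stoppers who attend the End of Study Visit are scanned there (Section 9.1.3.8) and so enter the FAS. Section 14.2.1 calls the FAS and PPS supportive, and the SAP may settle details. No OS input comes from the protocol.

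Most of this limits the reach of the point without answering it. The End of Study scan rescues only patients who live to attend it. Section 14.2.2.2 names the FAS and PPS, and no other set, for the secondary endpoints. A SAP censoring rule cannot restore vital status that was never collected, and the re-analysis after the Extension Phase does not lengthen off-drug follow-up.

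Three stronger readings are tempting but unsupported:
- *The curve fails at 6 months.* The scan schedule puts progression-driven censoring at about 7.4 months or later.
- *The 12-month bias reaches +6.4 points (35% PFS) or +9.1 (15% PFS).* Those figures arise only if drug stops at the instant of progression. Stopping at scheduled scans cuts them by about a third.
- *The late bias could be large and downward.* Values down to −16.9 points need the hazard of death to fall to 10% of its earlier level just as follow-up ends. Nothing in the protocol suggests that.

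**Conclusion.** The concern holds, with the analysis set as the main point. Running OS only in the FAS and PPS excludes patients who die or leave before any scan. Dropping the deaths raises OS from the start, by about 3 to 5.5 points at 6 months if 15% of PFS events are deaths without progression, and by 0 if there are none. Patients who leave alive and unscanned are also lost; their effect is not sized here.

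The follow-up limit is a minor, late problem. Follow-up is complete for all consenting patients to 6 months from first dose, and to about 7.4 months for those stopped at the Day 42 scan or later. Beyond that, the likely bias is upward and modest, and it is near zero if survival after progression is unrelated to time to progression.

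The sizes rest on assumed post-progression survival, frailty and unscanned deaths. The direction of the analysis-set effect for deaths follows from the text alone. The two-stage PFS decision is not affected.

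**What to change.** 1. **Analysis set (main change).** In Section 14.2.2.2, compute OS in all treated (Safety) or evaluable patients and name which; keep FAS and PPS results as supportive at most. The evaluable set has the advantage of the same denominator as the primary endpoint. This is wording only and needs no new data.

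2. **Reporting.** Give the Kaplan-Meier OS rate at 6 months from first dose, in that same set, as the main OS figure. Show the later curve labelled as subject to treatment-dependent censoring. This is also wording only; the cost is less weight on later OS.

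3. **Optional.** Follow consenting patients by the existing 3-monthly calls to one common calendar date, not tied to the end of the open-ended Extension Phase. This removes the follow-up bias in consenting patients. It needs an amendment, possibly a substantial one under Section 18.1, and perhaps re-consent. This version is dated 06 December 2017, after the planned end in the fourth quarter of 2016, so some vital status would be collected late. Patients who do not consent stay missing under any option. Given the small bias, the first two changes are enough if this one is not feasible.
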